## APPENDIX 4. GUIDELINES FOR WOMEN OF CHILDBEARING POTENTIAL AND FERTILE MALE SUBJECTS

For females of childbearing potential, defined as all premenopausal women capable of becoming pregnant, must agree to use a medically effective contraceptive method (has a failure rate of <1% per year) starting with the first dose of study drug through 6 months and 1 week (i.e., 25 weeks) after study drug discontinuation.

Postmenopausal women are defined as no menstrual periods for at least 12 consecutive months OR follicle-stimulating hormone (FSH) greater than 40 IU/L on at least two occasions.

Fertile male subjects, defined as all males physiologically capable of conceiving offspring, must agree to use a medically effective contraceptive method starting with the first dose of study drug through 3 months and a week (i.e., 13 weeks) after study drug discontinuation. This requirement applies to fertile male subjects who are sexually active with a female partner of child-bearing potential. Male subjects must also refrain from donating sperm during their participation in the study until 90 days after completing the study.

### Acceptable Contraception Methods:

Highly effective contraception is defined as:

True Abstinence	When this is in line with the preferred and usual lifestyle of the subject. Periodic abstinence (e.g., calendar, ovulation, symptothermal, post-ovulation methods) and withdrawal are not acceptable methods of contraception.
Sterilization	When a woman of childbearing potential has had surgical bilateral oophorectomy (with or without hysterectomy) or tubal ligation at least six weeks prior to study entry. In case of oophorectomy alone, only when the reproductive status of the woman has been confirmed by follow-up hormone level assessment.
Male Partner Sterilization	When the appropriate post-vasectomy documentation of the absence of sperm in the ejaculate.
Use of a combination of any two of the following (one from a and one from b):	
a) Placement of an intrauterine device (IUD) or intrauterine system (IUS) or established use of oral, injected, or implanted hormonal methods of contraception
 
b) Barrier methods of contraception: Condom or Occlusive cap (diaphragm or cervical/vault caps) with spermicidal foam/gel/film/cream/vaginal suppository.

### Unacceptable Contraception Methods:

Unacceptable contraception methods for women of childbearing potential include:

- IUD progesterone T
- Female condom
- Natural family planning (rhythm method) or breastfeeding
- Fertility awareness
- Withdrawal
- Cervical shield

## **APPENDIX 5. LYMPHOMA RESPONSE CRITERIA: MODIFIED LUGANO CLASSIFICATION**

### **SELECTION OF TARGET LESIONS**

Up to six of the largest dominant nodes or tumor masses selected according to all of the following:

1. Clearly measurable in two diameters (longest diameter [LDi] and shortest diameter) at baseline
  - a. All nodal lesions must measure >1.5 cm in longest diameter regardless of short axis measurement
  - b. All measurable extranodal lesions should have a longest tumor diameter >1.0 cm
2. All other lesions (including nodal, extranodal, and assessable disease) should be followed as nontarget lesions
3. If possible, the lesions should be from disparate regions of the body
4. Should include mediastinal and retroperitoneal areas of disease whenever these sites are involved

### **SELECTION OF NON-TARGET LESIONS**

Non-target lesions will be qualitatively assessed at each subsequent timepoint. All of the sites of disease present at baseline and not classified as target lesions will be classified as non-target lesions, including any measurable lesions that were not chosen as target lesions.

Examples of non-target lesions include:

1. All bone lesions, irrespective of the modality used to assess them
2. Lymphangitis of the skin or lung
3. Cystic lesions
4. Irradiated lesions
5. Measurable lesions beyond the maximum number of 6
6. Groups of lesions that are small and numerous
7. Pleural/pericardial effusions and/or ascites
  - a. Effusions, ascites, or other fluid collections will be followed as non-target lesions
  - b. At each assessment point, radiologists will check for the presence or absence of effusions/ascites. If there is a significant volume increase in the absence of a benign etiology, progression can be assessed
  - c. Significant new effusions, ascites, or other fluid collections, which are radiographically suggestive of malignancy should be recorded as new lesions and should be assessed

Response should be determined on the basis of radiographic and clinical evidence of disease. For subjects who achieve a CR by CT criteria, an FDG-PET will be performed. Assessment by PET should follow the criteria described by [Cheson 2014](#) which is summarized in [Table 7](#).

- Overall response should be determined based upon the Modified Lugano response criteria ([Table 8](#)).

### **Spleen Involvement**

- Splenomegaly defined as enlargement of spleen measured by vertical (cranial or caudal) length of >13 cm. Nodal measurable lesions can be followed as target, non-target, or new extra-nodal lesions.

### **Liver Involvement**

- CT measurements used for qualitative assessment of liver involvement, and FDG-PET used for assessment of response (e.g., new uptake indicative of disease progression). Nodal measurable lesions followed as target, non-target, or new extra-nodal lesions.

**Table 7: Revised Criteria for Response Assessment from Cheson et al. 2014**

Response Site	PET/CT—Based Response	CT-Based Response
Complete Response	Complete metabolic response	Complete radiologic response (all of the following)
Lymph nodes and extralymphatic sites	
 
Score 1, 2, or 3a with or without a residual mass on 5PSb
 
It is recognized that in Waldeyer's ring or extranodal sites with high physiologic uptake or with activation within spleen or marrow (e.g., with chemotherapy or myeloid colony stimulating factors), uptake may be greater than normal mediastinum and/or liver. In this circumstance, complete metabolic response may be inferred if uptake at sites of initial involvement is no greater than surrounding normal tissue even if the tissue has high physiologic uptake.
 
	
 
Target nodes/nodal masses must regress to <math>\leq 1.5</math> cm in LDi
 
No extralymphatic sites of disease
 

Nonmeasured lesions	
 
Not applicable
 
	
 
Absent
 

Organ enlargement	
 
Not applicable
 
	
 
Regress to normal
 

New lesions	
 
None
 
	
 
None
 

Bone marrow	
 
No evidence of FDG-avid disease in marrow
 
	
 
Normal by morphology; if indeterminate, IHC-negative
 

Partial Response	Partial metabolic response	Partial remission (all of the following):
Lymph nodes and extralymphatic sites	
 
Score 4 or 5b with reduced uptake compared with baseline and residual mass(es) of any size.
 
At interim, these findings suggest responding disease.
 
At end of treatment, these findings indicate residual disease.
 
	
 
<math>\geq 50\%</math> decrease in SPD of up to 6 target measurable nodes and extranodal sites
 
When a lesion is too small to measure on CT, assign 5 mm <math>\times</math> 5 mm as the default value
 
When no longer visible, 0 <math>\times</math> 0 mm
 
For a node <math>> 5</math> mm <math>\times</math> 5 mm, but smaller than normal; use actual measurement for calculation
 

Nonmeasured lesions	
 
Not applicable
 
	
 
Absent/normal, regressed, but no increase
 

Organ enlargement	
 
Not applicable
 
	
 
Spleen must have regressed by <math>> 50\%</math> in length beyond normal
 

New lesions	
 
None
 
	
 
None
 

**Table 7: Revised Criteria for Response Assessment from Cheson et al. 2014 (Continued)**

Response Site	PET/CT—Based Response	CT-Based Response
Bone marrow	
 
Residual uptake higher than uptake in normal marrow but reduced compared with baseline (diffuse uptake compatible with reactive changes from chemotherapy allowed). If there are persistent focal changes in the marrow in the context of a nodal response, consideration should be given to further evaluation with MRI or biopsy or an interval scan.
 
	
 
Not applicable
 

No Response or Stable Disease	No metabolic response	Stable disease
Target nodes/nodal masses, extranodal lesions	
 
Score 4 or 5 with no significant change in FDG uptake from baseline at interim or end of treatment
 
	
 
<50% decrease from baseline in SPD of up to 6 dominant, measurable nodes and extranodal sites; no criteria for progressive disease are met
 

Nonmeasured lesions	
 
Not applicable
 
	
 
No increase consistent with progression
 

Organ enlargement	
 
Not applicable
 
	
 
No increase consistent with progression
 

New lesions	
 
None
 
	
 
None
 

Bone marrow	
 
No change from baseline
 
	
 
Not applicable
 

Progressive Disease	Progressive metabolic disease	Progressive disease requires at least one of the following
Individual target nodes/nodal masses	
 
Score 4 or 5 with an increase in intensity of uptake from baseline and/or
 
	
 
PPD progression:
 

Extranodal lesions	
 
New FDG-avid foci consistent with lymphoma at interim or end-of-treatment assessment
 
	
 
An individual node/lesion must be abnormal with
 
LDi >1.5 cm and
 
Increase by <math>\geq 50\%</math> from PPD nadir and
 
An increase in LDi or SDi from nadir 
 
0.5 cm for lesions <math>\leq 2</math> cm
 
1.0 cm for lesions >2 cm
 
 
 
In the setting of splenomegaly, the splenic length must increase by >50% of the extent of its prior increase beyond baseline (e.g., a 15 cm spleen must increase to >16 cm). If no prior splenomegaly, must increase by at least 2 cm from baseline. New or recurrent splenomegaly
 

**Table 7: Revised Criteria for Response Assessment from Cheson et al. 2014 (Continued)**

Response Site	PET/CT—Based Response	CT-Based Response
Nonmeasured lesions	
 
None
 
	
 
New or clear progression of pre-existing nonmeasured lesions
 

New Lesions	
 
New FDG-avid foci consistent with lymphoma rather than another etiology (e.g., infection, inflammation). If uncertain regarding etiology of new lesions, biopsy or interval scan may be considered.
 
	
 
Regrowth of previously resolved lesions
 
A new node >1.5 cm in any axis
 
A new extranodal site >1.0 cm in any axis; if <1.0 cm in any axis, its presence must be unequivocal and must be attributable to lymphoma
 
Assessable disease of any size unequivocally attributable to lymphoma
 

Bone Marrow	
 
New or recurrent FDG-avid foci
 
	
 
New or recurrent involvement
 

Abbreviations: 5PS = 5-point scale; CT = computed tomography; FDG = F-fluorodeoxyglucose; GI = gastrointestinal; IHC = immunohistochemistry; LDi = longest transverse diameter of a lesion; MRI = magnetic resonance imaging; PET = positron emission tomography; PPD = cross product of the LDi and perpendicular diameter; SDi = shortest axis perpendicular to the LDi; SPD = sum of the product of the perpendicular diameters for multiple lesions.

a. Measured dominant lesions: up to six of the largest dominant nodes, nodal masses, and extranodal lesions selected to be clearly measurable in two diameters. Nodes should preferably be from disparate regions of the body and should include, where applicable, mediastinal and retroperitoneal areas. Non-nodal lesions include those in solid organs (e.g., liver, spleen, kidneys, lungs), GI involvement, cutaneous lesions, or those noted on palpation. Nonmeasured lesions: any disease not selected as measured, dominant disease and truly assessable disease should be considered not measured. These sites include any nodes, nodal masses, and extranodal sites not selected as dominant or measurable or that do not meet the requirements for measurability but are still considered abnormal, as well as truly assessable disease, which is any site of suspected disease that would be difficult to follow quantitatively with measurement, including pleural effusions, ascites, bone lesions, leptomeningeal disease, abdominal masses, and other lesions that cannot be confirmed and followed by imaging. In Waldeyer's ring or in extranodal sites (e.g., GI tract, liver, bone marrow), FDG uptake may be greater than in the mediastinum with complete metabolic response, but should be no higher than surrounding normal physiologic uptake (e.g., with marrow activation as a result of chemotherapy or myeloid growth factors).

b. PET 5PS: 1, no uptake above background; 2, uptake ≤ mediastinum; 3, uptake > mediastinum but ≤ liver; 4, uptake moderately > liver; 5, uptake markedly higher than liver and/or new lesions; X, new areas of uptake unlikely to be related to lymphoma.

**Table 8: Modified Lugano Response Criteria**

Morphologic Response	Metabolic Response	Bone Marrow Biopsy	Prior Combined Response	Lugano Combined Response
NE/No CT	CMR			CR
	PMR			SD unless the previous CT scan indicated CR or PR, then combined response is PR*
	NMR			SD
	PMD			PD
	NE/No PET			NE
PD	CMR			PD
	PMR			PD
	NMR			PD
	PMD			PD
	NE/No PET			PD
SD	CMR			CR
	PMR			SD*
	NMR			SD
	PMD			PD
	NE/No PET***			SD
PR	CMR			CR
	PMR			PR
	NMR			PR*
	PMD			PD
	NE/No PET***			PR
CR	CMR			CR
	PMR			PR
	NMR			PR
	PMD			PD
	NE/No PET		No prior PET response	PR
	NE/No PET		No prior response and prior PET was negative	CR
	NE/No PET		SD	PR
	NE/No PET		PR	PR
	NE/No PET		CR	CR
	NE/No PET		PD and prior evaluable PET was not PMD	PR
NE/No PET***		PD and prior PET was PMD	NE	
NE/No PET	CR**		CR	

Abbreviations: BMB = bone marrow biopsy; CMR = complete metabolic response; CR = complete response; CT = computed tomography; NE = not evaluated; NMR = no metabolic response; PD = progressive disease; PET = positron emission tomography; PMD = progressive metabolic disease; PMR = partial metabolic response; PR = partial response; SD = stable disease

\* Lugano combine response criteria for this response combination has been modified per FDA request.

\*\* When a PET scan is not acquired or not evaluable, a bone marrow biopsy (BMB) is required to confirm a CR by CT. If no BMB is taken (and no PET can be acquired for this time point), the best possible overall response is a PR unless the prior overall response meets either criteria: prior overall response was CR or there was no prior overall response and the baseline/prior PET was negative.

\*\*\* When a timepoint does not have an evaluable PET scan, the morphologic response is not PD, and the most recent evaluable PET scan indicated a metabolic response of PMD, then the combined response will be NE. An improved combined response without evidence that the findings in the prior PET scan have resolved isn't justified. However, there is not PET-based evidence that the subject has continuing PD, so the response is designated as NE.

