### 4.1. Inclusion Criteria

1. Signed informed consent.
2. Age  $\geq 18$  years (or age of majority).
3. Histologically confirmed diagnosis as defined in the World Health Organization (WHO) classification ([Swerdlow 2016](#)) of:
  - a. FL limited to Grade 1, 2, or 3a; or
  - b. MZL, including nodal, extranodal, and splenic MZL (histopathological report confirming diagnosis must be available during screening procedures).
4. Subjects with relapsed or refractory FL or MZL who received  $\geq 2$  prior therapy regimens. A previous regimen is defined as one of the following: at least two months of single-agent therapy or at least two consecutive cycles of polychemotherapy, autologous transplant, or radioimmunotherapy. Prior therapy must include an anti-CD20 monoclonal antibody (mAb) and an alkylating agent(s). Relapsed or refractory disease is defined as:
  - a. Relapsed disease: disease progression after a response (CR or PR) lasting  $\geq 6$  months
  - b. Refractory disease: no response to therapy (no CR or PR), or response lasting  $< 6$  months
5. At least one bi-dimensionally measurable nodal lesion  $> 1.5$  cm or extranodal lesions  $> 1$  cm in its longest diameter by computed tomography (CT) scan as defined by the Modified Lugano Classification ([Appendix 5](#)).
  - a. Previously irradiated lesions can be selected as target lesions only in cases of unequivocal evidence of progression.
  - b. For subjects with splenic MZL only: diffuse spleen involvement with splenomegaly, which is defined as the splenic vertical length greater than 13 cm.
6. Eastern Cooperative Oncology Group (ECOG) performance status of 0 to 1 ([Oken 1982](#); [Appendix 6](#)).
7. Adequate hematologic parameters at screening unless abnormal values are due to lymphoma per Investigator assessment:
  - a. Absolute neutrophil count (ANC)  $\geq 1.0 \times 10^9/L$  ( $\geq 1,000/mm^3$ )
  - b. Platelet count  $\geq 75.0 \times 10^9/L$  ( $\geq 75,000/mm^3$ )
8. Adequate renal and hepatic function per local laboratory reference range at screening as follows:

- a. Aspartate aminotransferase (AST)/serum glutamic-oxaloacetic transaminase (SGOT), alanine aminotransferase (ALT)/serum glutamic-pyruvate transaminase (SGPT)  $\leq 3.0 \times$  upper limit of normal (ULN)
  - b. Total bilirubin  $\leq 2.0 \times$  ULN or  $\leq 3 \times$  ULN for subjects with Gilbert's syndrome

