Disease/response assessment will be based on radiological tumor evaluation of neck, chest, abdomen, and pelvis by using IV (and oral, if indicated, per Imaging Manual) contrast enhanced CT/magnetic resonance imaging (MRI) and/or PET-CT imaging modalities at screening and at follow-up visits at the frequency described in the Schedule of Assessments ([Appendix 1](#)), and disease response will be based on the Modified Lugano Classification response criteria ([Appendix 5](#)). Please see [Table 7](#) for overall guidance on response assessment criteria based on Lugano Classification response criteria. In this clinical study, additional modifications to the Lugano Classification response criteria are incorporated per regulatory request to clarify rules for partial response (PR) assessment. These modifications highlight that morphologic (CT scan based) response will be the basis for PR assessment and not metabolic (FDG-PET scan) based assessment of response. Please see [Table 8](#) for details regarding combined response assessment criteria based on beforementioned modified Lugano Classification. For subjects followed by CT scans only, a bone marrow biopsy will be required to confirm a CR in a subject who achieve a morphologic CR by CT scan. To rule out a potential of false positive diagnosis of disease progression in ambiguous cases, it is highly recommended to repeat imaging assessments within 4-8 weeks after initial suspicion of PD. The Investigator's assessment of disease response will be used for subject management. For the final analysis of study efficacy endpoints, disease/response assessment will be performed by an IRRC blinded to Investigator assessment. For subjects with gastric MZL, endoscopy with biopsy must be performed to confirm CR.

Safety will be assessed by laboratory safety tests including hematology (complete blood count [CBC]), serum chemistry, and cytomegalovirus (CMV) using quantitative PCR; and clinical assessments including physical examination, vital signs, ECOG performance status, and 12-lead electrocardiogram (ECG). Adverse events will be graded according to National Cancer Institute Common Terminology Criteria for Adverse Events (NCI CTCAE) v5.0.

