# 7. RESPONSE ASSESSMENT AND STUDY ENDPOINTS

## 7.1. Overview

Efficacy assessments will be based on the Modified Lugano Classification response criteria ([Appendix 5](#)).

Response to treatment based on the Investigator evaluation of imaging tests will be the basis for subject management.

An IRRC composed of radiologists and oncologists will review all imaging tests, and clinical data if necessary, to determine disease response and progression. All radiographic images/scans will be sent by the study sites to the central imaging vendor and archived for potential future

evaluation (e.g., evaluation using Cheson criteria). The process for image collection and transmission to the central imaging vendor can be found in the Study Manual.

Tumor imaging (neck, chest, abdomen, and pelvis) should be performed by contrast-enhanced CT and/or FDG-PET scan. Because FL and MZL is typically (FDG)-avid, as per Modified Lugano Classification ([Appendix 5](#)) FDG-PET scan is the preferred method for disease/response assessment to confirm CR. If a combined/dual PET/CT scanner is the available modality, then the CT portion of a PET/CT may be used instead of a dedicated CT provided that the CT scan is performed with a high-resolution imaging quality to ensure optimal measurement for disease/response assessment. CT scans must be performed using intravenous (IV) contrast. For subjects who are intolerant to contrast agents, the CT scan will be performed with oral contrast or MRI scans will be used. If a PET/CT is not available or is not evaluable, bone marrow biopsy will be utilized to confirm a morphologic CR documented by CT scan. The imaging schedule is described in [Appendix 1- Response Assessment](#). In summary, imaging scans (CT scan or PET/CT scan) will be obtained with the following frequency:

- Every 2 months ( $\pm 7$  days) for the first 6 months on study
- Every 3 months ( $\pm 7$  days) for the next 12 months on study
- Every 6 months ( $\pm 14$  days) thereafter, starting with month 18

For subjects with gastric MZL, endoscopy with biopsy must be performed to confirm CR.

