### **7.2.1. Objective Response Rate (ORR)**

The primary efficacy endpoint is ORR as determined by the IRRC, defined as the proportion of subjects achieving the best response rating of CR or PR based on the Modified Lugano Classification. ORR will also be assessed by the Investigator as a secondary endpoint.

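### Table 8 scores stable disease on CT plus a complete metabolic response as CR without requiring FDG-avid disease at screening, so a never-avid, CT-stable subject would count in the primary ORR

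*Protocol*

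**What the plan says.** **Endpoint.** Protocol 7.2.1 gives ORR by IRRC as the primary endpoint, "defined as the proportion of subjects achieving the best response rating of CR or PR based on the Modified Lugano Classification". SAP 3.1 and 7.1 repeat this. No confirmatory scan is asked for, so a single qualifying read before first PD is enough.

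**Combination rule.** In Appendix 5, Table 8, morphologic SD with CMR gives CR, and NE/No CT with CMR gives CR. The cells for bone marrow and prior response are blank in both rows, and neither row refers to the screening PET.

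**Definition of CMR.** Table 7 requires a score of 1, 2 or 3, "with or without a residual mass on 5PS". Partial metabolic response is tied to baseline: a score of 4 or 5 "with reduced uptake compared with baseline and residual mass(es) of any size". No metabolic response is also defined by comparison with baseline. CMR is not.

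**Eligibility.** Inclusion criterion 5 (Protocol 4.1) asks for "At least one bi-dimensionally measurable nodal lesion", or an extranodal lesion, above a size threshold "in its longest diameter by computed tomography (CT) scan as defined by the Modified Lugano Classification". Splenic MZL may instead qualify by spleen length. No criterion asks for FDG uptake.

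**PET schedule.** Appendix 1 requires PET at screening and schedules it again at Days 121 and 365. A positive screening result is not required. Protocol 7.1 says only "Because FL and MZL is typically (FDG)-avid".

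**Negative baseline PET.** The double-starred footnote to Table 8 mentions it once: "there was no prior overall response and the baseline/prior PET was negative". That footnote concerns CR on CT when no evaluable PET exists at the timepoint.

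**The concern.** CMR is meant to show that avid disease has stopped being avid. Because Table 7 sets no baseline condition, it can also be met by disease that never took up FDG. Such a subject may have had less than a 50% reduction in SPD, yet moves from SD on CT straight to CR.

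The reading then counts in the IRRC ORR, the CR rate and the DOR analysis set (SAP 4.3). It may also persist, because Appendix 1 says PET is no longer needed once CMR has been reached.

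This matters because ORR is the only primary endpoint of a single-arm study that the SAP links to an NDA filing. The error runs in one direction: it can add responders but cannot remove any. Neither the protocol nor the SAP contains an avidity rule or a sensitivity analysis that would show its effect.

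**Working it through.** **1. Path through the tables.** Take a subject who enters on CT-measurable nodes, has a negative screening PET, develops no new avid foci, and has SD on CT at Day 121.
- Table 7: score 1 to 3, hence CMR.
- Table 8: SD + CMR, hence CR.
- Protocol 7.2.1: best response CR, hence a responder.

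The NE/No CT + CMR row gives the same result when CT is missing. The PR + CMR row does not affect ORR, because PR already counts. It affects only the CR rate.

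**2. Reproduce the FL design (Protocol 11.1, SAP 2.4).** Inputs: n = 91, null 48%, alternative 65.5%, one-sided alpha 0.025, power at least 90%.
- P(X ≥ 53 | 91, 0.48) = 0.0321, which exceeds 0.025.
- P(X ≥ 54 | 91, 0.48) = 0.0196, so the pass mark is 54/91 = 59.3%.
- P(X ≥ 54 | 91, 0.655) = 0.910, so the stated power holds.
- The SAP's Clopper-Pearson interval agrees: the 95% lower bound is 48.5% at 54/91 and 47.4% at 53/91.

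**3. Effect on the FL test.** Let q be the share of subjects who are PET-negative at screening, CT-stable and otherwise non-responders. The documents give no value for q, so it is an assumption. With a true ORR of 48%, the observed rate is 0.48 + q and P(pass) = P(X ≥ 54 | 91, 0.48 + q).

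| Assumed q | Expected subjects (91 × q) | P(pass) at true ORR 48% |
|---|---|---|
| 0 | 0 | 0.0196 |
| 1% | 0.9 | 0.031 |
| 2% | 1.8 | 0.046 |
| 3% | 2.7 | 0.068 |

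**4. A milder calibration.** Suppose exactly m subjects are false responders and the other 91 − m respond at 48%. Then P(X ≥ 54 − m | 91 − m, 0.48) is 0.0248, 0.0312, 0.0390 and 0.0483 for m = 1 to 4. One subject leaves the error just under 0.025, and two take it above. This version does not hold the true ORR at the null: it falls to 0.48 × 90/91 = 47.5% for m = 1 and 0.48 × 87/91 = 45.9% for m = 4. The table in step 3 is therefore the cleaner statement of type I error.

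**5. At the boundary.** If one of 54 counted responders came only through this path, removing it leaves 53/91 = 58.2%. The lower bound of 47.4% no longer excludes 48%.

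**6. MZL.** Protocol 11.1 now describes the 32 subjects as giving preliminary data. Each false responder adds 1/32 = 3.1 points to ORR.

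**The case against.** **The IRRC Charter may settle it.** The protocol places IRRC methods in a charter that is not among the documents, and a charter could instruct readers to treat PET as non-contributory when nothing was avid at baseline. This stands. What can be said is that the protocol and SAP contain no such rule. If the charter has one, it reverses an explicit Table 8 cell and should appear there too.

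**The text can be read more kindly.** Table 8 mentions a negative prior PET as something apart from CMR. One clause in Table 7 refers to sites of initial involvement, and Protocol 5.1 mentions subjects followed by CT only. These suggest that PET-negative subjects might belong in the CT rows, but no passage sends them there.

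**CR by PET despite stable CT is the design.** This also stands. For disease that was avid at baseline, SD + CMR = CR is not disputed. A reader might infer a conflict with the protocol's intent to rely on CT, since Protocol 5.1 says "morphologic (CT scan based) response will be the basis for PR assessment and not metabolic (FDG-PET scan) based assessment of response". That sentence covers PR only, and Protocol 7.1 prefers PET for confirming CR. The starred regulator-requested changes do not touch SD + CMR, which fits acceptance of that row as well as oversight.

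**The footnote is not the defect.** A reader might take "there was no prior overall response and the baseline/prior PET was negative" as the faulty rule. It still requires CR on CT, so it shows only that a negative baseline PET was contemplated.

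**Part of this will be visible.** SAP 7.1 plans waterfall plots of IRRC-measured SPD change, which would show responders with less than 50% shrinkage. They would not show which of those were PET-negative at screening.

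**Conclusion.** The concern holds as a gap in the written rule. Under the protocol and SAP, a subject without avid disease at screening, without new avid foci and with SD (or no evaluable CT) is scored CR and enters the primary ORR, the CR rate and the DOR set.

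The size is unknown. The number of such subjects is not given, and with both diseases described as typically avid it may be small or zero. If q is 1% to 3% of the FL primary efficacy population, the chance of passing at a true ORR of 48% is 0.031 to 0.068. At the boundary, one subject decides the result. In MZL the effect is 3.1 points per subject on a descriptive estimate.

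A reader might infer that the reported ORR is inflated, or that MZL is distorted by several subjects. The documents support neither, because both need a PET-negative share that is not stated. Nor can bias against the 48% benchmark itself be judged, since the response criteria behind the published rates are not given.

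Severity: should-fix. Confidence: moderate, mainly because the IRRC Charter could not be checked.

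**What to change.** 1. Check whether the IRRC Charter already has an avidity rule.
2. State the same rule in Appendix 5 (Table 8) and in SAP 3.1 and 7.1. Suggested content: SD + CMR and NE/No CT + CMR give CR only if the screening PET showed FDG-avid lymphoma. Otherwise later metabolic response is treated as NE/No PET and the CT rows apply, with new avid foci still giving progressive metabolic disease.
3. Enrolment is closed (Protocol 8.3). If the primary derivation cannot be changed at this stage, leave it as it is. Report the number of subjects PET-negative at screening, and prespecify a sensitivity ORR, CR rate and DOR that do not count responses resting only on CMR without baseline avidity.

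**Cost.** One rule in two documents (and in the charter if it is absent there), plus a re-derivation from existing IRRC reads. No new scans or subjects are needed and the sample size does not change. The downside is that ORR and the CR rate may be slightly lower.
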